10.6 Handling of Multiplicity

Pairwise comparisons between each ABBV-8E12 dose group and the placebo group will be performed with two-sided tests. Hochberg procedure² will be used for the efficacy analysis to handle multiplicity of comparisons between multiple ABBV-8E12 doses and placebo at the pre-specified significance level at the interim analysis ($\alpha = 0.00001$ at each futility interim analysis), which is described in the DMC Charter.

[figure not shown]
For the final analysis, a graphic approach³ will be used to control overall family wise error rate due to multiple comparisons for primary and key secondary efficacy endpoints for multiple ABBV-8E12 doses. The overall α for the final analysis is 0.04998 after accounting for α spending at interim futility analyses. This α will be split equally between two dose groups to test the efficacy endpoints in the primary and key secondary families within each dose level at Week 52. The order of efficacy endpoints to be tested is PSPRS

total score change at Week 52, UPDRS-II score change at Week 52, CGI-C score at Week 52, midbrain atrophy measured by volumetric MRI change from baseline at Week 52, SEADL score change at Week 52 (Table 3). The primary endpoint will be tested first followed by the secondary endpoints and α could be propagated between two doses and two families of hypotheses testing based on the graphic approach (Figure 2). In the graph, the arrows specify the α transfer paths. Once an endpoint is rejected (i.e., deemed significant) at its assigned significance level, its significance level will be transferred to subsequent endpoint(s) following the arrow(s). If more than one arrow originates from an endpoint, the significance level for this endpoint (once rejected) will be split between multiple subsequent endpoints following the arrows. The numbers on the arrows denote the weights for transferring and (possibly) splitting significance levels. Specifically, the weight 1 denotes 100% transfer of significance level. The number underneath of each hypothesis is the original weight for α splitting assigned to the hypothesis. The overall type I error rate for this trial will be controlled at the two-sided 5% level. Nominal P values and multiplicity adjusted P values for all variables listed in Table 3 will be presented in a table.

Table 3. Hypotheses Testing Order in The Graphical Testing Approach

Efficacy Endpoints Family	Ordered Efficacy Endpoints	Hypotheses	
		The High Dose (4000 mg) vs. Placebo	The Low Dose (2000 mg) vs. Placebo
Primary family	PSPRS total score change from baseline at Week 52	H ₁₁	H ₂₁
Secondary family	UPDRS Part II score change from baseline at Week 52	H ₁₂	H ₂₂
	CGI-C score at Week 52	H ₁₃	H ₂₃
	Midbrain atrophy measured by volumetric MRI change from baseline at Week 52	H ₁₄	H ₂₄
	SEADL score change from baseline at Week 52	H ₁₅	H ₂₅

Figure 2. A graph for multiplicity adjustment of multiple hypotheses

10.7 Efficacy Subgroup Analysis

To examine whether gender, age group (≤ 65 vs > 65 year old), disease severity (\leq vs $>$ median of PSPRS baseline total score which is rounded to the closest multiple of 5. E.g., if the median is 38.5 then the median cut off will be 40.), and geographical region (North America including US and Canada, European countries plus Australia, and Japan) have an impact on response to treatment, subgroup analyses on PSPRS total score will be conducted on change from baseline to final. Subgroup analyses will be performed using an ANCOVA model with the terms of treatment, subgroup variable, site (site nested within a region will be used for subgroup analysis by geographical region), the treatment-by-subgroup variable interaction, and baseline score as a covariate. The hypothesis that consistent response to treatment across strata of a subgroup variable will be tested at the

significance level of 0.100 by examining the *P* value of the treatment-by-subgroup interaction term in the ANCOVA model specified above. The statistical comparison of each ABBV-8E12 dose group with placebo within each subgroup stratum will be performed when the statistical significance of the treatment-by-subgroup interaction term is achieved at 0.100 level. The subgroup analysis will be conducted on the ITT dataset.

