8.1.4 Subgroup Analysis of PSPRS Total Score

To examine whether gender, age group, study site, country/region or other baseline variables have an impact on response to treatment, subgroup analyses on PSPRS total score will be conducted on change from baseline to last observations up to Week 52. Subgroup analyses will be performed using an ANCOVA model with the terms of treatment, site, subgroup variable, the treatment-by-subgroup variable interaction, and baseline score as a covariate. The subgroup analysis for country/region will be performed using the same model but with the study site nested within country/region. The hypothesis that consistent response to treatment across strata of a subgroup variable will be tested at the significance level of 0.100 by examining the *P* value of the treatment-by-subgroup interaction term in the ANCOVA model specified above. The statistical comparison of each ABBV-8E12 dose group with placebo within each subgroup stratum will be performed when the statistical significance of the treatment-by-subgroup interaction term is achieved at 0.100 level. The subgroup analysis will be conducted in the ITT data set.

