10.2 Primary Analysis of Primary Efficacy Endpoint

The primary efficacy endpoint is the change from baseline to Week 52 visit on the PSPRS total score. The primary analysis population will be subjects in the ITT dataset and the primary analysis will be a likelihood-based, mixed-effects model, repeated measures (MMRM) analysis of the change from baseline to each post-baseline assessment up to and including Week 52. The model will include fixed, categorical effects for treatment, site, visit, baseline score-by-visit and treatment-by-visit interactions, with continuous fixed

covariates for baseline score. The primary comparison will be the contrast between each ABBV-8E12 dose group and placebo group at Week 52. Contrasts between each ABBV-8E12 dose group and placebo at Weeks 12, 24, and 36 and overall across the treatment period will be obtained and will be considered as secondary. An unstructured (co)variance structure will be used to model the within-patient errors. If this analysis fails to converge, compound symmetry (co)variance structures will be tested. The same (co)variance structure will also be used for all MMRM analyses for secondary efficacy variables. Satterthwaite's approximation will be used to estimate denominator degrees of freedom.

The following statistics will be presented on the statistical table of MMRM analysis for change from baseline to each visit (Weeks 12, 24, 36, and 52): descriptive statistics (number of non-missing observations, mean, standard deviation, minimum and maximum) for each treatment group. LS mean and standard error within group will be presented for each treatment group. LS mean, standard error, 95% confidence interval and two-sided nominal *P* value of treatment difference comparing each ABBV-8E12 dose group with placebo will also be presented for each post-baseline visit. The LS mean, standard error, 95% confidence interval and two-sided nominal *P* value of treatment difference comparing each ABBV-8E12 dose group with placebo across the treatment period will be included in the output as well.

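### SAP 10.7 tests whether baseline severity and age modify the PSPRS effect only after cutting each variable in two; a continuous interaction test would usually be more sensitive, and none is planned

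*SAP*

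**What the plan says.** Protocol 8.1.4 sets the aim: "To examine whether gender, age group, study site, country/region or other baseline variables have an impact on response to treatment". It gives no cut points.

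SAP 10.7 supplies them. Age is "age group (≤ 65 vs > 65 year old". Severity is split at the "median of PSPRS baseline total score which is rounded to the closest multiple of 5", so the severity cut depends on the sample and can lie up to 2.5 points from the median. The outcome is also fixed there: "subgroup analyses on PSPRS total score will be conducted on change from baseline to final".

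The model is an ANCOVA with treatment, subgroup, site, "the treatment-by-subgroup variable interaction, and baseline score as a covariate". The interaction is tested at 0.100, and dose-placebo comparisons within strata are made only if it is significant. Baseline PSPRS therefore stays continuous as a main effect, while its interaction with treatment is tested only in two-level form.

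The primary MMRM in SAP 10.2 does not fill the gap: "The model will include fixed, categorical effects for treatment, site, visit, baseline score-by-visit and treatment-by-visit interactions". It has no treatment-by-baseline term and no age term.

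**The concern.** The question is whether the drug effect varies along two measured scales, PSPRS from 0 to 100 and age in years. A two-level split treats everyone on one side of the cut as alike. If the effect changes gradually, part of the signal is thrown away.

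Interaction tests in a trial sized for main effects are weak to begin with. A further loss makes a real gradient with severity or age easier to miss. Because the interaction P value also decides whether within-stratum comparisons are run, a miss removes the formal comparisons that might have shown the pattern. What is at stake is how well a secondary question is answered, not the confirmatory result.

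**Working it through.** **Inputs from the documents.** 110 per arm, 330 in all, 1:1:1 (SAP 4.3). Interaction alpha 0.100 and three arms, hence a 2-df interaction (SAP 10.7). The outcome is change to the final observation, so close to all 330 subjects can contribute.

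**Assumed, because the documents do not say.** A normal moderator. A 4000 mg effect that changes by *g* SD of PSPRS change per SD of the moderator, with half that slope for 2000 mg. SD of baseline PSPRS between 8 and 15. The percentile of age at which 65 falls.

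**The plan's own figure.** No power is stated for any subgroup test. The stated primary power of about 90% does reproduce for the high dose: 110 × 0.75 = 82.5 per arm with data, effect size 0.56, two-sided 0.025, gives 91.2%. The sample-size basis is therefore sound to build on.

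**Step 1: information kept by a cut.** For a cut *c* SD from the mean of a normal variable, the fraction kept is φ(c)² / [Φ(c)(1 − Φ(c))].
- Severity, exact median: 0.3989² / 0.25 = 0.637 (2/π), a loss of 36.3%.
- Severity, cut 2.5 points off the median: with SD 15, c = 0.167, a loss of 37.0%; with SD 8, c = 0.3125, a loss of 38.6%.
- Age, cut fixed at 65: the minimum loss is 36.3%, if 65 happens to be the median. It is 37.8% if 40% of subjects are 65 or younger, 42.4% if 30%, and 51.0% if 20%.
- Uniform moderator cut at its median: a loss of 25%.

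**Step 2: power by slope.** With slopes b = (g, g/2) and covariance S = [[2,1],[1,2]]/110, the non-centrality is b′S⁻¹b = (110/3)(2 − 1 + 0.5)g² = 55g². Multiply by 0.637 for a median split and compare with the 0.90 quantile of chi-square on 2 df (4.605).

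| g | Continuous | Median split | Loss (points) |
|---|---|---|---|
| 0.10 | 16.4% | 14.1% | 2.4 |
| 0.14 | 22.7% | 18.0% | 4.6 |
| 0.20 | 35.7% | 26.5% | 9.2 |
| 0.28 | 57.1% | 41.7% | 15.4 |
| 0.35 | 74.8% | 56.8% | 18.0 |
| 0.42 | 87.8% | 71.3% | 16.5 |
| 0.56 | 98.5% | 91.3% | 7.2 |

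**Step 3: power by strength of the continuous test.** For a median split the loss is 3.7 points when the continuous test has 20% power, 7.3 at 30%, 10.6 at 40%, 17.9 at 80%, 12.4 at 95% and 6.0 at 99%. If 65 is the 30th percentile of age, the loss over the 40-95% range is about 12 to 22 points.

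**Step 4: simulation.** The SAP's ANCOVA was simulated with 330 subjects, 40 site levels (assumed) and 3,000 runs per setting. For severity, the losses were 3.0, 14.6, 17.9 and 18.1 points at g = 0.14, 0.28, 0.35 and 0.42. For age cut at its 30th percentile they were 5.2, 16.2, 20.9 and 23.9. The closed form is not misleading.

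**The case against.** The strongest reply is that every figure depends on assumptions the documents do not supply. That stands. Eligibility limits severity (able to walk 5 steps, symptoms under 5 years, MMSE at least 15), so a full normal range is not guaranteed; a normal truncated at ±1.5 SD would lose about 30%. If the effect truly steps at the cut, splitting costs little.

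The slopes behind the larger losses are also not small. Against the planned effect of 0.56, g = 0.28 means the effect vanishes 0.56/0.28 = 2 SD from the mean, and g = 0.35 means it vanishes at 1.6 SD. For modest modification both tests are weak and the change recovers little.

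The protocol itself names age group, the age cut and the rule for the severity cut are prespecified, and strata are easy to read. That is a good reason to keep them for display. It does not make them the better test.

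A reader might infer several stronger things that the documents do not support:
- That 36% applies to both variables. It is a median-split figure, and age is cut at a fixed 65, so for age it is only a floor under normality.
- That 10-18 points is the general cost. It holds only over the range of gradients given above.
- That a non-significant interaction will be reported as proof of consistency. SAP 10.7 names consistency as the null hypothesis; it does not say that non-rejection establishes it.
- That the interaction test decides everything reported by subgroup. It gates only the statistical comparisons within strata.

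**Conclusion.** The point holds as a modest improvement. Effect modification by severity and age is tested only through two-level cuts, and no continuous interaction is planned in Protocol 8.1.4, SAP 10.2 or SAP 10.7.

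Under a roughly normal moderator and a linear gradient, the loss of information is about 36-39% for severity and at least 36% for age (about 42% if 65 is the 30th percentile). At alpha 0.100 with 110 per arm, a median split costs about 2-5 points of power for g = 0.10-0.14 and about 10-18 points when the continuous test would have roughly 40-95% power. The age cut can cost more if 65 is far from the median.

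None of this touches the primary or key secondary claims: the subgroup tests are not among the hypotheses in SAP Table 3.

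**What to change.** In SAP 10.7, test effect modification by severity with a treatment-by-continuous baseline PSPRS term, and by age with a treatment-by-continuous age term (adding continuous age as a main effect), each at the existing 0.100 level. Report the estimated dose-placebo difference at the quartiles of each variable. Keep the two-level splits for descriptive display.

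The cost is a sentence or two in the SAP and a few model terms on data already collected. No subjects or visits are added, and no confirmatory test changes. The downside is small: the continuous term assumes an approximately linear gradient and can be sensitive to extreme baseline values. The retained display would still show a step at the cut.

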In addition, a histogram will be generated to describe the proportion of subjects in each PSPRS response category for each treatment group. The 1-point interval response categories are defined based on PSPRS total score change from the baseline to final starting from the minimum to the maximum of the change score (e.g., ...; $-5 < \text{to} \leq -4$; $-4 < \text{to} \leq -3$; $-3 < \text{to} \leq -2$; $-2 < \text{to} \leq -1$; $-1 < \text{to} \leq 0$; $0 < \text{to} \leq 1$; $1 < \text{to} \leq 2$; $2 < \text{to} \leq 3$;).

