10.4.2 Combination of Sites with Fewer Than 2 Subjects per Treatment Group

When "site" is included as a factor in a statistical model for the interim or final analyses, Japan is considered as one site because randomization is stratified by country for Japan. In countries other than Japan, sites that do not have at least 2 subjects per treatment group for the ITT dataset will be combined within each country as follows.

1. Divide the sites into 2 groups with Group 1 including all sites that have at least 2 subjects per treatment group and Group 2 including all remaining sites. Sort each group in ascending order by total sample size and investigator number.
2. Starting at the top of the Group 2 list (i.e., the first site with the smallest sample size), combine the minimum number of sites required to achieve a pseudo-site that has at least 2 subjects per treatment group. Continue this process until all Group 2 sites have been grouped into pseudo-sites.
3. If there is a site (or sites) left after Step 2, combine this site (or sites) with the last pseudo-site that is created. For the situation where there is no previous pseudo-site exists, combine this site (or sites) with the first site on the sorted Group 1 list.

The naming of the pseudo-sites will be given by xxx99901, xxx99902, etc., where xxx is the country code.

The combined pseudo-sites will be used in all statistical models that include the "Site" as a factor. However, the original site identification will be used in all summaries of subject disposition or discontinuation by Study Site and in all data listings. In the summaries of the number and percentage of subjects contributed by each site in each treatment group for the ITT dataset, the name of pseudo-sites will also be displayed.

10.5 Handling of Missing Data for Efficacy Assessments and Sensitivity Analysis of the Primary Efficacy Endpoint

Missing Items for a Rating Scale

Unless otherwise specified, when a total or domain score of an efficacy measure is calculated from a set of individual items, the total or domain score will be considered missing if any of the individual items are missing. When an average score is obtained from a set of individual items, it will be calculated from the non-missing items. Missing items will be imputed specifically for the following scales:

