14.0 Summary of Changes

There are some changes in the planned analyses from the protocol (original protocol, protocol Amendment 1, Amendment 2, Amendment 3, Amendment 4) to Statistical Analysis Plan version 1.0. The multiplicity adjustment method using Dunnet's test at interim analyses have changed to using Hochberg procedure in Amendment 3 and in the current SAP. Detailed multiplicity adjustment method is added in protocol Amendment 3 and is reflected in Section 10.6 for multiplicity method change in the SAP. The sample size increase from 180 (in protocols prior to Amendment 3) to 330 (Amendment 3) and including Japan in Study M15-562 are reflected in the current SAP. These changes are reflected in Section 4.3. Analysis of the primary efficacy variables and safety variables analysis by geographical region are included in Section 10.7 and Section 11.0 of the current SAP, respectively.

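### PSPRS subgroup results come from a last-observation ANCOVA rather than the Week 52 model, and no stratum estimate is promised unless a weak interaction test is significant

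*SAP*

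**What the plan says.** SAP 10.7 names four subgroup variables: gender, age group, baseline severity (split at the median PSPRS score, rounded to a multiple of 5) and geographical region. It says that "subgroup analyses on PSPRS total score will be conducted on change from baseline to final", by ANCOVA with treatment, subgroup, site, treatment-by-subgroup interaction and baseline. For region, "site nested within a region will be used for subgroup analysis by geographical region". SAP 6.2 defines *final* as the last non-missing value within 45 days of the last dose. The interaction is tested at 0.100, and the comparison of each dose with placebo "within each subgroup stratum will be performed when the statistical significance of the treatment-by-subgroup interaction term is achieved at 0.100 level". The section lists no other stratum output. Protocol 8.1.4 has the same method but a different list: it includes study site, and *other baseline variables* in place of severity.

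The primary analysis in SAP 10.2 is an MMRM: "The primary comparison will be the contrast between each ABBV-8E12 dose group and placebo group at Week 52". Its listed outputs include "LS mean, standard error, 95% confidence interval and two-sided nominal" P value. Protocol 8.1.3.2 plans an overall ANCOVA on change to the final observation. SAP section 10 does not carry it forward; its overall display of change to final is a histogram ("The 1-point interval response categories are defined based on PSPRS total score change from the baseline to final"). SAP 14.0 points to 10.7 for regional efficacy: "Analysis of the primary efficacy variables and safety variables analysis by geographical region are included in Section 10.7".

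**The concern.** There are two problems.

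- **Time point.** SAP 4.3 assumes that 25% have no Week 52 data. For them the subgroup analysis uses an earlier value, while the primary contrast is at Week 52. A regional or severity result cannot be laid beside the primary estimate, and the SAP has no overall last-observation analysis to lay it beside instead.
- **Reporting.** The only stratum result that 10.7 commits to depends on a significant interaction. If the test is not significant, the report may contain one P value per subgroup and nothing else, and that P value may be read as showing a consistent effect. This matters most for region, because SAP 4.3 sizes Japan with regional consistency in mind and 10.7 is where regional efficacy is analysed.

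**Working it through.** **Inputs (SAP 4.3).** 110 per arm; effects 0.28 SD (low dose) and 0.56 SD (high dose); 25% with no Week 52 data; 8 Japanese subjects per arm; regional shares 7%, 54% and 39%, which give about 8/59/43 per arm. SD is set to 1.

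**The plan's own figure.** Evaluable subjects: 110 × 0.75 = 82.5 per arm. For the high dose at two-sided 2.5%: 0.56 × √(82.5/2) = 3.60; 3.60 − 2.24 = 1.36; power 91%. This agrees with the stated figure of about 90%, so the SD scale is used as the plan uses it.

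**Interaction test at 0.100.** The arm effects 0, 0.28 and 0.56 have squared deviations from their mean of 2 × 0.28² = 0.1568. If one stratum (n₁ per arm) has no effect and the rest (n₂ per arm) have the full effect, the noncentrality is λ = 0.1568 × n₁n₂/(n₁+n₂). Power comes from the noncentral F distribution with 4 df for region and 2 df for a two-level subgroup.

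- Japan, no effect: λ = 0.1568 × 8 × 102/110 = 1.16.
- Europe/Australia, no effect: λ = 0.1568 × 43 × 67/110 = 4.11.
- One half of a 55/55 split, no effect: λ = 0.1568 × 55 × 55/110 = 4.31.

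**Shrinkage from using the last observation (assumption).** If the effect grows linearly and the SD stays at 1, the retained fraction is 0.75 + 0.25 × (mean week of last observation)/52. Dropouts in equal thirds at Weeks 12, 24 and 36 give 0.75 + 0.25 × 24/52 = 0.865. The extremes are 0.808 (all at Week 12) and 0.923 (all at Week 36). λ is multiplied by the square of this fraction.

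| True pattern | Significant, no shrinkage | Significant, effects × 0.865 |
|---|---|---|
| Consistent effects | 10% | 10% |
| Japan half the effect | 12% | 12% |
| Japan no effect | 19.5% | 17% |
| Japan reversed | 49% | 40% |
| Europe/Australia no effect | 45% | 36% |
| 55/55 split, one half no effect | 57% | 47% |
| 55/55 split, one half with half the effect | 23% | 19% |

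Across the shrinkage extremes, the Japan no-effect figure runs from 16.1% to 18.0%.

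**Precision if every stratum is reported.** The 95% CI half-width is 1.96 × √(2/n) in SD units, first with all randomised and then with 75%: Japan 0.98 (n = 8) to 1.13 (n = 6); North America 0.36 to 0.42; Europe/Australia 0.42 to 0.48; one half of an even split 0.37 to 0.43.

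**Chance of a wrong-sign Japan estimate when effects are consistent.** The high-dose SE is √(2/8) = 0.50, so the probability is Φ(−0.56/0.50) = 13%, or about 17% with the effect shrunk by 13%.

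**The case against.** **The trigger guards against over-reading small strata.** This has force. A reader might infer that the trigger makes misleading Japan results common. In simulation with consistent effects, the Japan high-dose estimate does have the wrong sign in 27-30% of the trials where the interaction is significant. But that happens in only 10% of trials, so a wrong-sign Japan estimate reaches the report this way in about 3% of all trials, against 13-17% if it is always shown. Selection is therefore not the argument for change. The argument is that a non-significant test says little, and an interval shows how little.

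**Reporting does not fix the Japan sample size.** This is true. If Japan has no effect, its 95% CI excludes 0.56 SD in 16% (6 per arm) to 20% (8 per arm) of trials, no better than the interaction test. The gain is greater in the larger strata.

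**The endpoint was pre-specified.** Protocol 8.1.3.2 plans an overall final-observation ANCOVA, and 10.7 can be seen as its extension. That answers any charge of an arbitrary choice, but the SAP omits the overall analysis, and the primary claim is at Week 52.

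**The shrinkage is overstated.** If the variance also grows over time, the standardised effect shrinks less, by about 4-11% in an illustration. The answers still lie inside the ranges in the table.

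Two other stronger readings are not supported. The SAP does not forbid stratum estimates: it says when comparisons will be made and is silent otherwise. Nor can the documents show that the Japan sizing criterion fails, since Method 2 is specified by citation to a source outside them.

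**Conclusion.** The point holds as an alignment and reporting gap in a supportive analysis. The mismatch of time point and model is plain on the text. The weakness of the interaction test rests on the SAP 4.3 effects and shares, SD = 1 and illustrative patterns of heterogeneity. Under these it misses a null effect in Japan in at least 80% of trials, and a null effect in one half of an even split in roughly half of them (43-53%). A reader might infer that the efficacy conclusion or error control is at risk. It is not: the subgroup analyses lie outside the multiplicity procedure in SAP 10.6, and the primary test is untouched. The change is worth making because it is cheap and uses data already collected.

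**What to change.** Amend SAP 10.7 for its four listed subgroups:

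- Report the Week 52 dose-minus-placebo estimate with 95% CI for every stratum, whatever the interaction P value. Show that P value alongside and label the results descriptive and outside the family-wise error control.
- Take the estimates from the primary MMRM with subgroup, subgroup-by-visit, treatment-by-subgroup and treatment-by-visit-by-subgroup terms added. For region, nest site within region; this fits SAP 10.4.2, where "Japan is considered as one site because randomization is stratified by country for Japan".
- Keep the last-observation ANCOVA as supportive.

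Do not extend this to the study-site subgroup in Protocol 8.1.4: 330 subjects over about 60 sites is 5.5 per site, or fewer than 2 per arm. Because the protocol's ANCOVA is kept, a SAP change recorded in SAP 14.0 should suffice.

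The cost is wording and modest programming, with no extra patients or data. The downside is that more unadjusted stratum results are shown and that the Japan estimates are very imprecise and will sometimes point the wrong way by chance. The report should say so beside them.
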